### Assumptions for modelling the number of PEs

- For the number of PEs a negative binomial distribution is assumed, which can be fitted with PROC GENMOD using a loglinear model to estimate the parameters  $\theta_1$  (regression coefficients  $\beta$  for treatment arms and for covariates and dispersion parameter c).
- The imputation will assume the same patient effect in Periods 1 and 2.
- The unobserved events  $Y_2$  conditional on  $Y_1$  will be imputed from the negative binomial distribution with, using the SAS language for the RAND function, number of successes  $k^*$  and probability of success  $p^*$ :

$$k^* = \frac{1}{c} + Y_1$$
 and  $p^* = (\frac{1}{c} + \psi_1) / (\frac{1}{c} + \psi_1 + \psi_2)$ 

where:

$$\psi_1 = T_1 * EXP(x^T \beta)$$
 and  $\psi_2 = T_2 * EXP(x^T \beta)$  as described by (Keene et al., 2014).

- Simulated PEs will have a duration of 0 days for simplification.
- The negative binomial model is used to analyze the observed data in period 1 and the imputed datasets with period 1+2 data.

CONFIDENTIAL Page 113 of 139

### MI under MAR assumption: (e.g., Schafer, 1999)

Within the MI approach the missing data is imputed multiple times using the following two steps:

- Step 1: Simulate the parameters  $\theta_1$  from the posterior distribution, given the observed data  $Y_{Obs}$ .
- Step 2: Simulate the missing data from the conditional distribution of missing data, given the simulated parameters from Step 1 and the observed data:

$$Y_{mis} \sim P(Y_{mis}|Y_{obs},\theta_1)$$

Each imputed dataset is analyzed with PROC GENMOD. Results are combined with PROC MIANALYZE.

### Tipping point analysis under MNAR assumptions:

For a tipping point analysis, the MI approach is modified: After Step 1 the parameter  $\psi_2$  is adjusted, reducing treatment effects before imputing the missing data in Step 2. Thus, imputations are done assuming smaller treatment effects in the missing data, and it can be checked which decrease in treatment effects would change a significant result into a non-significant result.

The analysis of imputed datasets with PROC GENMOD and the combined analysis with PROC MIANALYZE remain unchanged, only the imputations in Step 2 are modified under the assumption of reduced treatment effects.

### **Computations for Step 1:**

Samples from the posterior distribution can be drawn with the BAYES statement in PROC GENMOD based on only the observed data, which applies an iterative algorithm. After a sufficient number of "burn-in" iterations (NBI=200), an appropriate number of samples from the posterior distribution are simulated (NMC=100) and can be saved into a dataset:

CONFIDENTIAL Page 114 of 139

```
*--- Merge posterior samples with observed data ---;

PROC SQL;

CREATE TABLE _40join AS

SELECT *

FROM _16keepTrt, _25bayes

ORDER BY _imputation_, usubjid
;

QUIT;
```

The above statements simulate 100 values of  $\theta_1 = (\beta, c)$  in dataset \_25bayes given the observed data on PEs which can then be used in Step 2 to create 100 imputed datasets. Further,  $\psi_1$  and  $\psi_2$  can be calculated and the dispersion parameter c obtained at the same time.

The values for  $\theta_1$  in row k of \_25bayes are used to impute the missing values in the k-th imputed dataset.

### **Computations for Step 2:**

For Step 2 the unknown value  $Y_2$  has to be sampled from the conditional distribution given the observed values  $(Y_1, T_1)$  and the generated parameters from step 1.

```
SAS-Code:

Y2 = RAND('NEGBINOMIAL', P_STAR, K_STAR);
```

Each imputed dataset is then analyzed with PROC GENMOD based on the loglinear Negative Binomial model, and the resulting estimates for  $(\beta, c)$  and their standard errors are combined using PROC MIANALYZE to get a combined estimate with a corresponding standard error for each parameter:

CONFIDENTIAL Page 115 of 139

```
*--- combine results with MIANALYZE ---;

PROC MIANALYZE data=_60ests;

MODELEFFECTS lbetaestimate;

STDERR stderr;
by label;
ODS OUTPUT PARAMETERESTIMATES=_65est;

RUN;
```

### **Modified procedure for tipping point analysis:**

A modified Step 2 is needed to implement the reduced treatment effects under the MNAR scenarios. To reduce differences due to simulation errors it is suggested to use the same underlying set of random numbers for the MAR scenario and for each MNAR scenario as follows:

- Use the same set of simulated parameters (from **Step 1**) generated for the MAR scenario also for all MNAR scenarios.
- Multiply  $\psi_2$  with the corresponding adjustment factors for each MNAR scenario (i.e., decreased  $\psi_2$  in the placebo arm, increased  $\psi_2$  in the brensocatib arms).

The SAS-Code with macro variable that describes the adjustment is (The magnitude of the adjustment is defined in Section 8.2.2):

```
PSI2 Adj = PSI2 * &adjust.
```

• Simulate the number of PEs  $Y_2$  for Period 2 based on:

```
Y2 = RAND('NEGBINOMIAL', P_STAR_Adj, K_STAR); where p^* has been updated to reflect the adjusted \psi_2.
```

The above steps will ensure that differences between MAR and MNAR scenarios are mainly due to the systematic differences between the different MNAR adjustments and not just the result of simulation errors.

CONFIDENTIAL Page 116 of 139

### **Secondary Endpoint: Time to first PE – Main analysis**

### **Cumulative first PE incidence rates over the 52-Week treatment period:**

```
PROC LIFETEST DATA=<dataIn> METHOD=KM TIMELIST=(12,24,36,52) REDUCEOUT;
  TIME ttpe * cnsr(1);
  STRATA trt;
RUN;
```

#### Where:

```
ttpe time to the first PE event (in weeks) cnsr censoring flag (1=censored, 0=event)
```

trt participants treatment (brensocatib 25mg, brensocatib 10mg,

placebo)

For the incidence rates the survival probability will be subtracted from 1. For the KM estimate at weeks 12, 24, and 36, the survival probability will be displayed.

### Covariate-adjusted Cox proportional hazards regression model:

#### RUN;

#### Where:

```
trtp participants treatment (1=brensocatib 25mg, 2=brensocatib 10mg, 3=placebo)

region1 stratification factor: region1

psaecol stratification factor: sputum sample being classified as positive or negative for Pseudomonas aeruginosa at screening visit

numpes stratification factor: number of prior Pes [<3 or ≥3] in the previous 12 months

ttpe time to the first PE event (in weeks)

agegr3 adult, adolescent
```

Sorting: data will be sorted by region1, psaecol, numpes, agegr3, ttpe, and usubjid

CONFIDENTIAL Page 117 of 139

# Secondary Endpoint: Time to first PE – Tipping Point (Sensitivity Analysis)

NOTE: Steps 2 to 5 will be repeated varying delta (δ) for Brensocatib and Placebo. As described in step 3, &\_delta\_a and &\_delta\_p will be macro variables set to the delta adjustments for Brensocatib and Placebo respectively. Delta = 1 reflects no delta adjustment.

**Step 1:** Create a dataset named tte containing 1 row per participant and the following variables

```
usubjid participants identifier

trtn participants treatment (1=brensocatib 25mg, 2=brensocatib 10mg, 3=placebo)

region1 stratification factor: region

psaecol stratification factor: sputum sample for Pseudomonas aeruginosa at Screening Visit (1=positive or 0=negative)

numpes Stratification factor: number of prior Pes in the previous 12 months (1= <3, 0= ≥3)

agegr3 age group: adult, adolescent

ttpe Time to first pulmonary exacerbation event

cnsr Censoring flag (1=censored, 0=event); NOTE: participants with intercurrent events will be censored.
```

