# 10.4.6.1.3. Sensitivity Analyses for Primary Endpoint

Sensitivity analyses will be conducted to assess the robustness of the primary results in the presence of missing data.

In the event that there are study participants who discontinue randomized IP early and also decline to remain in the study, ascertainment of data will be incomplete, and a true treatment policy/ITT analysis cannot be achieved. A MAR assumption for the missing data is made implicitly for the On-Study estimand using the observed data alone, and a hypothetical strategy is inherently implemented for the ICEs of early study withdrawn.

The main analysis using the negative binomial model is unbiased under the MAR assumption for the missing data. However, in some instances, the fact that data are missing may be directly related to the unobserved values (ie, MNAR). Therefore, robustness of the main analysis to departures from the MAR assumption will be assessed using tipping-point analyses. Due to the inherent difficulties in identifying the missing data mechanism in practice, all missing data will be assumed MNAR, and the tipping-point penalties will be applied accordingly.

Full details of the sensitivity analyses will be described in the SAP.

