#### **6.2.1.** Identification of ICEs

The following subsections will describe the two ICEs defined for this study.

If both ICEs occur at the same date, e.g., early discontinuation from randomized IP and modification from standard of care at the same date, the early discontinuation from randomized IP will be prioritized. Within standard of care the discontinuation from standard of care will be prioritized over addition of new chronic antibiotics.

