#### 6.7.1.6. Time to First Pulmonary Exacerbation

The time to first exacerbation event confirmed through adjudication will be calculated as

```
Time to first PE (days) = CEC assessed onset date of first PE - date of reference* + 1.
```

\*For the On-Study Estimand the date of reference will be the date of randomization, while for the On-Treatment Estimand the date of reference will be the date of first IP administration (see Sections 6.4.1 and 6.7).

Participants who do not have a PE confirmed through adjudication during the 52-week treatment period or for whom the first PE is recorded beyond Week 52 visit will be censored at the date of Week 52 (or at the date of EOS for participants early discontinued from study) visit for the On-Study Estimand and at the date of last IP intake or the date of first ICE onset for the On-Treatment Estimand. Participants randomized but not treated will not be analyzed for the On-Treatment Estimand but censored at the day of randomization.

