## 8.3. Secondary Endpoints

#### **8.3.1.** Time to First Pulmonary Exacerbation

#### 8.3.1.1. Main Analyses

The Main Estimand of the time to first PE is the On-Study Estimand in which all observed data will be included in the analysis (see Section 2). The ITT Analysis Set (see Section 5.2) will be used for this Estimand. The derivation of the endpoint is detailed in Section 6.7.1.6.

Cumulative first PE incidence rates over the 52-Week treatment period will be calculated using the Kaplan-Meier method. The summary will include the number of participants with at least 1 PE and the number of participants without any events (censored). A covariate-adjusted Cox proportional hazards regression model including fixed effects for treatment group, sputum sample being classified as positive or negative for *Pseudomonas aeruginosa* at Screening Visit, the number of prior PEs [<3 or ≥3] in the previous 12 months, stratification region (North America, Europe, Japan, and the Rest of the World), and age group (adult, adolescent) will be fitted using the PHREG procedure with the robust sandwich estimate for the covariance matrix in SAS (option COVSANDWICH(AGGREGATE) in the procedure-statement). If the age group covariate creates estimability issues, it may be removed. If the model still does not converge after removing the age group covariate, other handling including using the parametric covariance estimator instead of the robust sandwich covariance estimator may be applied. The CLASS statement will identify covariates while the model will be identified in the MODEL statement. Results will be summarized in a table including number and percentage of participants with PEs, estimated hazard ratio and 95%

CONFIDENTIAL Page 57 of 139

confidence limits. The 2-sided Wald p-value from the Cox model will be compared to the appropriate alpha level per the multiple test procedure. Technical details for the implementation in SAS can be found in Appendix I.

Kaplan-Meier estimates of the median including 95% confidence interval will be presented.

The effect over time will be illustrated with a plot of the complement (1 - Kaplan-Meier) estimates).

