#### 8.3.1.2. Sensitivity Analyses

The analysis of time to first PE over the 52-Week treatment period is planned to be performed under the assumption that observations that are censored prior to Week 52 are censored-at-random (CAR) and that censoring is uninformative; meaning that censoring times and event times are independent. There is no plan to impute missing event times in the main analysis.

A tipping point analysis will be used as a sensitivity analysis to examine the effect of potential departures from the CAR assumption, e.g., censored-not-at-random (CNAR), in the main analysis. Due to the inherent difficulties in identifying the missing data mechanism in practice, all missing data (i.e., censoring prior to Week 52) will be assumed CNAR, and the tipping point penalties will be applied accordingly.

As the first step, an additional penalty (delta) will be applied to the assumed hazard rates for the CNAR data. For each brensocatib dose comparison relative to placebo, the tipping point penalties (delta adjustment) will be applied in a bi-directional manner. That is, the hazard rate for the CNAR data in the brensocatib arms will be incrementally increased. This worsening outlook is quantified by a sensitivity parameter  $\delta$  interpreted as an increased hazard of PE event post-dropout, while the hazard rate for the CNAR data in the placebo arm will be incrementally decreased. This process of incrementing the penalties will continue until the respective comparison is no longer statistically significant (i.e., the Tipping Point) per the multiple testing procedure described in Section 6.3 or until the unlikely incremented/decremented hazard rate has been achieved.

As the second step, MI of the missing first PE event times under the hazard rate assumptions will be implemented using Cox model. Post study withdrawal first PE event times will be imputed conditional upon hazard rate assumptions. The process of imputing the first PE missing event times will be repeated multiple times to create 100 separate data sets. If the imputed first event times are greater than 52 weeks, the participants will be censored at Week 52.

With each increment, the 100 complete data sets will each be analyzed using the same model as for the main analysis. The analysis results for each increment will be combined using Rubin's rules (Rubin 1987).

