#### PROC SQL;

```
PROC SORT DATA=tte5 (RENAME=(ttpe=pred_ttpe)) OUT=tte6;
BY trtn region1 psaecol numpes agegr3 usubjid n_surv DESCENDING p_surv;
RUN;
```

```
DATA tte7;
   SET tte6;
   BY trtn region1 psaecol numpes agegr3 usubjid n_surv DESCENDING p_surv;
   IF LAST.usubjid THEN OUTPUT;
RUN;
```

The variable pred\_ttpe is the new predicted Time to Pulmonary Exacerbation event.

Step 4: Using the original tte dataset, replace any participants censored prior to Week 52 as identified using ttpe and cnsr, with the pred\_ttpe from the above process, updating their censoring flag to be an event. Note: this will create 100 datasets separately for each delta tipping point. Each of the datasets will be analyzed using a cox proportional hazards model outputting the parameter estimate and standard error for the trtn (Active vs Placebo) comparison (for example - into pe1 to pe100).

CONFIDENTIAL Page 120 of 139

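### The Appendix I note for the time-to-first-PE tipping point censors participants with intercurrent events, against the On-Study rules it should follow; separately, the severe-PE tipping level inherits the primary endpoint's 0.01

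*SAP*

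**What the plan says.** **Estimand.** SAP 8.3.1.1 states: "The Main Estimand of the time to first PE is the On-Study Estimand in which all observed data will be included in the analysis". SAP Table 2 gives treatment policy for both ICEs under this estimand, and SAP 6.2 keeps observed data whether or not the participant remains on IP.

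**What an ICE is.** SAP 6.2.1: "The following subsections will describe the two ICEs defined for this study". Its subsections cover early discontinuation of randomized IP and modification of standard of care, meaning chronic antibiotics. Study withdrawal is not listed.

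**Censoring.** Under SAP 6.7.1.6, On-Study participants without an adjudicated PE "will be censored at the date of Week 52 (or at the date of EOS for participants early discontinued from study"). The same section uses ICE onset as a censoring date only for the On-Treatment estimand.

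**Tipping point, main text.** SAP 8.3.1.2: "Post study withdrawal first PE event times will be imputed conditional upon hazard rate assumptions". The grid stops when the comparison is "no longer statistically significant (i.e., the Tipping Point) per the multiple testing procedure described in Section 6.3", or at an implausible hazard rate.

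**Tipping point, Appendix I.** Step 1 defines the censoring flag and adds "NOTE: participants with intercurrent events will be censored", with no censoring date. Step 4 tells the programmer to "replace any participants censored prior to Week 52 as identified using ttpe and cnsr", using the predicted time.

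**Severe PEs.** SAP 8.3.4.2 applies the approach of 8.2.2. That section sets the tipping level at two-sided 0.01 and refers to the Section 6.3 procedure.

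**The concern.** Appendix I is the programming specification. Steps 1 and 4 together, read with the SAP's own ICE definition, build a dataset in which someone who stopped IP or changed a chronic antibiotic, stayed in follow-up and then had a first PE loses that observed event. It is replaced by a draw from a model, with a hazard penalty whenever delta is not 1. The Step 2 model is fitted to the same dataset, so post-ICE experience drops out of the fit as well.

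Three things are at stake. The grid would no longer test the On-Study result it is meant to stress. Its delta = 1 cell would not correspond to the main Cox analysis, as the equivalent cell in SAP 8.2.2 does for the primary endpoint. And the penalties would fall on people whose outcomes are known, not only on those with missing follow-up. SAP 6.6 says post-IP data are collected so that the On-Study estimand can be analysed on full data; the note would set those data aside.

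The severe-PE issue is separate. A result can be significant under Section 6.3 and still count as tipped before any penalty is applied.

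**Working it through.** **1. The texts side by side**

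| Question | Table 2, 6.2, 6.7.1.6, 8.3.1.2 | Appendix I, Steps 1 and 4 |
|---|---|---|
| Does an ICE cause censoring under On-Study? | No | Yes |
| Is a first PE after an ICE kept? | Yes | No; replaced by an imputed time |
| Who is imputed? | Those who left the study | Everyone flagged as censored before Week 52 |

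The neighbouring specifications agree with the middle column. The primary-endpoint imputation covers only time off study (Appendix I, Table 19). The FEV1 analysis uses all recorded data to Week 52 (8.3.3.2). The Appendix I dataset for the responder endpoint names early study discontinuation as the reason for censoring.

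**2. Design inputs.** The plan gives no figure for this point, so its sample-size inputs are used (Protocol 10.1): placebo rate 1.2, ratio 0.70 (active rate 0.84), dispersion 1, 540 per arm. They reproduce the stated 90% power:

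- SE = √{[(1/1.2 + 1) + (1/0.84 + 1)]/540} = √(4.024/540) = 0.0863
- |ln 0.70|/SE = 0.3567/0.0863 = 4.13
- Power at two-sided 0.005 = Φ(4.13 − 2.81) ≈ 0.907

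**3. First PEs lost.** With dispersion 1, the chance of no PE by time t (years) is S(t) = 1/(1 + λt), with density f(t) = λ/(1 + λt)². Assume a share d has an ICE by Week 52 at constant hazard h = −ln(1 − d), that follow-up continues, and that censoring is at ICE onset. Then

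share lost = ∫₀¹ f(t)(1 − e^(−ht)) dt ÷ [1 − S(1)]

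with 1 − S(1) = 0.545 (placebo) and 0.457 (active).

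| d (assumed) | Placebo: share (of 540) | Active: share (of 540) |
|---|---|---|
| 5% | 1.9% (about 6) | 2.0% (5) |
| 10% | 3.8% (11) | 4.1% (10) |
| 20% | 7.8% (23) | 8.4% (21) |

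**4. Effect on the hazard ratio.** This was simulated with 400,000 per arm. Assumptions: 10% leave the study, a further 5, 10 or 20% have an ICE but stay, and times are uniform. Imputation used eight-interval piecewise-constant hazards, and imputed times beyond Week 52 were censored at Week 52.

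- *Participants imputed:* about 7% under 6.7.1.6 and 8.3.1.2; roughly 10-20% under the note.
- *Delta = 1, benefit persists after the ICE:* 0.767 / 0.765 / 0.764 under 6.7.1.6 against 0.766 / 0.764 / 0.768 under the note. No material change.
- *Delta = 1, benefit lost after the ICE:* main Cox 0.767 / 0.774 / 0.780 against 0.763 / 0.765 / 0.762. Differences are 0.004, 0.009 and 0.018, with the note looking slightly more favourable.
- *Illustrative penalised cell (hazard × 1.3 active, × 0.7 placebo; benefit persists):* 0.784 / 0.783 / 0.783 (p = 0.005) against 0.794 / 0.801 / 0.819 (p = 0.008 / 0.010 / 0.021). The note makes the result look less robust. These are raw p-values scaled to 540 per arm, ignoring between-imputation variance.

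**5. Severe-PE level.** Take raw p = 0.02 for 25 mg severe PEs (H9), all other raw p-values 0.0001. Under SAP 6.3.2, H9 alone gives 0.02. Paired with a 10 mg hypothesis from Families 2-6, the local p-value is 2 × 0.0001 = 0.0002; paired with the 10 mg primary hypothesis it is 2 × min(0.0001/1.9, 0.02/0.1) ≈ 0.0001. The adjusted p is the maximum, 0.02: significant at 0.05, yet tipped at 0.01 with delta = 1. If both doses have raw p = 0.02, the adjusted p is 2 × 0.02 = 0.04, with the same outcome.

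**The case against.** The best defence is that the note is a stray comment in a variable list and that the governing text is clear. On this view the author meant study withdrawal. Protocol 10.4.6.1.3, also a missing-data section, says "a hypothetical strategy is inherently implemented for the ICEs of early study withdrawn", and the near-identical responder code names study discontinuation. That may well be the intent. But SAP 6.2.1 does not define ICE that way, the note gives no date, and two programmers could build different datasets from it. The sentence needs correcting on either reading. The signed data review report in SAP 6.2 records agreed actions for ICEs but does not amend the note.

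It is also fair that the effect is small and every ICE rate is assumed. That limits the weight of the point but does not remove the contradiction.

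Three stronger readings are tempting, and the documents do not support them:

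- *That the severe-PE tipping level has no link to Section 6.3.* It has one: 8.3.4.2 imports 8.2.2, which cites Section 6.3. Only the inherited 0.01 is at issue.
- *That FEV1 and QoL-B are tipped on unadjusted p-values.* SAP 8.3.3.2 says two-sided 0.05 without saying which p-value. SAP 8.1 places all superiority comparisons under Section 6.3, and 6.3.2 rejects on adjusted p-values, so 0.05 can be read as the level for the adjusted p. The distinction has content: raw p-values of 0.04 and 0.03 for the two doses give 2 × 0.03 = 0.06. But this calls only for clarification.
- *That every participant with an ICE loses any PE, including one before the ICE.* No estimand in the SAP does that, so the sizes here assume censoring at ICE onset.

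**Conclusion.** The contradiction is real. As worded, the Appendix I note applies ICE censoring to an analysis whose estimand, censoring rule and imputation rule all exclude it, and Step 4 carries that into replacement of observed first PEs.

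Its size is modest: about 2-8% of first PEs replaced and a delta = 1 hazard-ratio shift of at most about 0.02. This rests on 5-20% of participants having an ICE but staying in the study, censoring at ICE onset, and the plan's design rates. If benefit is lost after the ICE, the active-arm share reaches about 10% at the top of that range. The direction is not fixed: penalised cells look less robust, while the delta = 1 cell can look slightly better if benefit fades.

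A reader might infer that the time-to-first-PE result itself or Type I error control is compromised. Neither is: the note touches only a sensitivity analysis, and 6.2 runs that only after a significant main result.

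The severe-PE level is a smaller, separate inconsistency. SAP 6.3 sets 0.01 for the primary endpoint alone.

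**What to change.** Replace the Step 1 note with:

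> Censoring follows Section 6.7.1.6 (On-Study): participants without an adjudicated PE are censored at the Week 52 visit, or at EOS if they left the study early. ICEs do not cause censoring, and PEs observed after an ICE are kept as events. Delta-adjusted imputation applies only to participants who left the study before Week 52 without a PE (Section 8.3.1.2).

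Read Step 4 with that last restriction. As a programming check, confirm that the delta = 1 cell agrees with the main Cox result apart from imputation noise.

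In 8.3.4.2, state that the severe-PE tipping point is reached when the Section 6.3 adjusted p-value exceeds 0.05, and that the 0.01 in 8.2.2 does not carry over. As a clarification, say in 8.3.3.2, and so for 8.3.5.2, that 0.05 applies to the Section 6.3 adjusted p-value.

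The cost is a few SAP sentences before database lock, with no new data. The one consequence to accept is that FEV1 and QoL-B tipping points may look less favourable than on raw p-values when the other dose does not clear its own tests.
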